- Official Title: CLINICAL, RADIOGRAPHIC, AND HISTOMORPHOMETRIC ANALYSIS OF ASTRA TECH IMPLANT EV PLACED AND IMMEDIATELY PROVISIONALIZED INTO PRESERVED ALVEOLAR RIDGES: A PROSPECTIVE 3-YEAR OUTCOMES STUDY
- NCT Number: NCT04255342
- Document Date: August 9, 2024

Objective: The objective of this study is to compare and evaluate the stability of the implant body, survival rate, bone-level changes, and the implant's soft-tissue outcomes over a period of 1 year.

Design: This study is a cohort study (*ClinicalTrials.gov identifier- NCT04255342*). The study population consists of adults aged 18-95 years old who are seeking care at the University of Iowa, College of Dentistry and Dental Clinics. Eligibility for the study included needing an implant placement and final crown delivery at the site of a single-rooted tooth that had previously undergone tooth extraction with bone grafting.

Methods: At least 3 months after tooth removal and bone grafting, consented subjects will undergo implant placement and immediate loading with a temporary crown. More specifically, a dental implant will be placed using Azentro, a commercially-available product that uses computer technology to plan the dental implant placement using the AstraTech Implant System EV and an immediate implant temporary crown will be placed using Azentro. After 3-months, a definitive all-ceramic crown will be placed that was made using a digital workflow. Participants will have a 1-year follow-up visit after placement of the definitive all-ceramic crown, specifically for data collection.

Statistical Analysis Plan: The volumetric and linear data obtained from the CBCT scans will be analyzed using the same test utilized for the histomorphometric data analyses, setting the significance level at 0.05. The Bonferroni method for correction will be applied and the false positive rate will be calculated. Wound Healing Index (WHI) values obtained will be analyzed using the Kruskal-Wallis test. The null hypothesis states that no differences in WHI will be found at different time points. Likewise, the self-reported level of discomfort and PROMs will be compared using the Kruskal-Wallis test. The level of discomfort and the post-op visits will be the dependent and independent variable respectively. The significance level will be set at 0.05. Other clinical variables recorded in this study will be presented using descriptive statistics (i.e., ITVs, marginal bone levels, and peri-implant mucosal outcomes). Nonetheless, the data will be assessed upon collection and suitability of appropriate analyses will be determined upon data distribution.

The specific variables that will be analyzed are as follows:

- Ability to place and provisionalize the implant following a completely digital protocol (e.g., Azentro)
- Modified Wound Healing Scale
- PROM data on post-surgical discomfort
- Satisfaction with temporary crown and gum tissue
- Stability of implant during osseointegration healing phase
- Ability to use Azentro digital file to fabricate definitive implant crown prosthesis
- Patient-reported outcome measures of satisfaction collected at 2-week, 6-week, Final Crown Delivery, 1-Year Visit)
- Clinical measure of peri-implant inflammation (probing depths, bleeding upon probing, keratinized gingiva, gingival index, plaque index)

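### Does the unnamed test and uncounted Bonferroni family for the CBCT data, which the variable list leaves out, require a change to the plan?

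*Combined protocol and SAP*

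**What the plan says.** The official title announces a "CLINICAL, RADIOGRAPHIC, AND HISTOMORPHOMETRIC ANALYSIS". The Objective is to "compare and evaluate the stability of the implant body, survival rate, bone-level changes" and soft-tissue outcomes over 1 year. The Methods describe implant placement, a temporary crown, a definitive crown and a 1-year visit. They mention neither CBCT nor histomorphometry.

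The Statistical Analysis Plan opens with the CBCT data, which "will be analyzed using the same test utilized for the histomorphometric data analyses, setting the significance level at 0.05". It continues: "The Bonferroni method for correction will be applied and the false positive rate will be calculated". The only test it names, Kruskal-Wallis, is assigned to the wound healing index, discomfort and the patient-reported outcomes. Other clinical variables "will be presented using descriptive statistics (i.e., ITVs, marginal bone levels, and peri-implant mucosal outcomes"). The paragraph closes by saying that "the data will be assessed upon collection and suitability of appropriate analyses will be determined upon data distribution".

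A list then follows under the words "The specific variables that will be analyzed are as follows". It has eight items: digital placement, wound healing, discomfort, satisfaction with the temporary crown, implant stability, use of the digital file for the final crown, satisfaction over time, and clinical signs of peri-implant inflammation. None is a CBCT or histomorphometric measure.

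**The concern.** Three things look wrong when the paragraph and the list are read together.

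- The plan promises a significance test on CBCT data, then gives a list of analysed variables without them.
- The test is defined by pointing to another analysis that is not described, so a reader cannot say what it is.
- Bonferroni controls the error rate only over the comparisons that k counts, and k is not given. It could be counted per measure, per data type (volumetric, linear) or over all CBCT comparisons.

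If these choices were made after the results were seen, CBCT p-values could be reported or dropped, and the threshold made looser or stricter, without departing from the text. At stake would be the credibility of any CBCT finding called significant.

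**Working it through.** **Inputs.** The significance level, 0.05, and the use of Bonferroni come from the Statistical Analysis Plan. The plan gives no number of measures, time points or contrasts, so there is no derived figure to reproduce. For illustration, assume one volumetric and two linear measures with two contrasts each, which makes six comparisons.

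**Step 1: chance of at least one false positive, six independent true nulls.**

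- One family, k = 6: 1 − (1 − 0.05/6)^6 = 1 − 0.9510 = 4.9%.
- Per data type, k = 2 and 4: 1 − (1 − 0.025)^2 × (1 − 0.0125)^4 = 1 − 0.9506 × 0.9509 = 9.6%.
- Per measure, k = 2: 1 − (1 − 0.025)^6 = 1 − 0.8591 = 14.1%.

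With no correction at all the figure would be 1 − 0.95^6 = 26.5%, so every reading of the Bonferroni sentence removes a large part of the problem.

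**Step 2: correlated measures.** Volumetric and linear readings from the same scans would plausibly be correlated. With equally correlated normal test statistics:

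| Correlation | One family | Per data type | Per measure |
|---|---|---|---|
| 0 | 4.9% | 9.6% | 14.1% |
| 0.5 | 4.1% | 7.9% | 11.3% |
| 0.8 | 2.8% | 5.4% | 7.5% |

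With one volumetric and one linear measure (four comparisons) and independence, one family gives 4.9% and per-measure counting 1 − 0.975^4 = 9.6%. With a single comparison there is no effect.

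**Step 3: which reading is natural.** The correction sentence directly follows a sentence whose subject is the volumetric and linear CBCT data together. Nothing divides them into sub-families. That points to one family, the column that stays below 5%.

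**Step 4: is the list a contradiction?** Set it against the rest of the document. Marginal bone levels are to be presented descriptively but are not in the list. Survival is in the Objective but not in the list. The list does not say it is exhaustive, and it visibly is not. The absence of CBCT is one more omission from an incomplete list, and does not cancel the CBCT sentence.

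**Step 5: would fixing one named test be a gain?** The obvious candidate is a paired t-test with no normality pretest. The documents do not say what the CBCT data measure or whether scans are repeated in a patient, so it may not even fit the design. Simulation does not favour banning the pretest either. For exponential within-patient changes with true mean zero, tested at 0.05:

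| Procedure | n = 20 | n = 30 |
|---|---|---|
| Shapiro-Wilk, then Wilcoxon if non-normal | 13.6% | 15.9% |
| Wilcoxon always, no pretest | 13.4% | 15.8% |

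The excess is the same without the switch. It arises because a zero mean in a skewed distribution is not the Wilcoxon null. The fixed paired t-test, run at 0.05/6 = 0.83%, rejected 3.4% and 2.6% of the time, three to four times its nominal level (3.4/0.83 = 4.1; 2.6/0.83 = 3.1). It would not deliver the clean family-wise rate that is the reason for prescribing it.

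**The case for a change.** The strongest case for a change is that the repair is cheap. A few lines would say whether CBCT is still an outcome, name the measures and the test, and state k, with no extra patients or visits. The closing sentence on data distribution also leaves the test open until the data are in hand, and Bonferroni cannot protect against a family chosen afterwards.

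The facts behind this stand: test, measures and k are not prespecified, and nothing suggests that the text was removed or blacked out. A tidier document would state them.

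What does not stand is the step from there to a fault in the plan. It goes too far to say the correction cannot be computed. Once the CBCT comparisons are made, k is known, 0.05/k follows, and so does the false positive rate the plan promises. A report that gives unadjusted p-values and the number of comparisons lets any reader apply a different k. The larger error rates need assumed counts together with a less natural way of counting. The freedom to leave CBCT results out is real, but it is not shown to reach any listed variable, and the bone-level part of the Objective can be met by marginal bone levels, which are descriptive.

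**Conclusion.** The gap is real but small, and no change to the plan is needed. An analyst would sensibly treat all CBCT comparisons as one family, divide 0.05 by their number and report that number. This keeps the family-wise rate at or below 5%, provided each test holds its own level: 4.9% for six independent comparisons, 2.8% at a correlation of 0.8. The figure of 14.1% requires six comparisons, independence and k counted per measure, and the documents support none of these. The variable list is incomplete and does not conflict with the CBCT sentence. The one specific method that might be imposed, a fixed paired t-test, presumes a design the documents do not describe and is not shown to be better. The document describes a cohort study and states no sample size, power or decision rule, and none of its conclusions is shown to turn on the CBCT p-values.

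The judgement rests on the single-family reading and on CBCT not being the study's main outcome, which fits its absence from both the Objective and the list. If a report were to count k per measure, or rest its main claim on a CBCT p-value, the point would deserve a second look then.

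### Holm's method, used within whatever family Bonferroni was meant to cover, keeps the same 5% family-wise bound and never rejects fewer hypotheses

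*Combined protocol and SAP*

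**What the plan says.** All the relevant text is in the Statistical Analysis Plan paragraph of the combined document and the list that follows it.

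- CBCT: "The volumetric and linear data obtained from the CBCT scans will be analyzed using the same test utilized for the histomorphometric data analyses", with the level given as "setting the significance level at 0.05". The test itself is not named.
- The next sentence reads: "The Bonferroni method for correction will be applied and the false positive rate will be calculated".
- Kruskal-Wallis tests of the Wound Healing Index (WHI), discomfort and patient-reported outcomes (PROMs) come after that. For these the level is stated again ("The significance level will be set at 0.05") and no correction is mentioned.
- Marginal bone levels are to be described only.
- The paragraph ends: "Nonetheless, the data will be assessed upon collection and suitability of appropriate analyses will be determined upon data distribution".
- The closing list, introduced by "The specific variables that will be analyzed are as follows", contains no CBCT item, so the number of CBCT tests cannot be counted from it.

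**The concern.** Bonferroni compares every p-value with 0.05 divided by the number of tests. Holm's step-down method relaxes that threshold after each rejection and has the same family-wise guarantee. A plan that uses Bonferroni for testing alone therefore gives up some power in exchange for simpler confidence intervals.

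This has some relevance here. Changes in bone level are part of the stated objective, yet marginal bone levels receive no test. Apart from the histomorphometric analysis that the paragraph refers to, CBCT is the only imaging or bone measurement for which it describes a formal test. The documents do not say what the CBCT scans measure or when they are taken, so the link to the objective is an inference.

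Two related points affect the same sentence. The divisor is undefined, and because analyses may be chosen after the data are seen, it could be settled late. Also, the second half of the sentence promises a quantity that, read literally, one data set cannot supply.

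**Working it through.** **Inputs.** From the plan: level 0.05 and Bonferroni. Not in the plan, so assumed: two-sided tests with normal statistics; m = 2 or 3 tests; power of 80% or 50% for each real effect tested alone at 0.05; correlation 0, 0.5 or 0.8 between tests. The plan has no power or sample-size figure to reproduce.

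**Error bound.** Bonferroni: m × 0.05/m = 0.05. Holm compares the i-th smallest p-value with 0.05/(m − i + 1) and stops at the first failure. The thresholds are 0.025 and 0.05 for m = 2, and 0.0167, 0.025 and 0.05 for m = 3. Suppose m0 nulls are true. The first true null that Holm reaches has rank at most m − m0 + 1, so its threshold is at most 0.05/m0. The chance that any true null falls below that is at most m0 × 0.05/m0 = 0.05, whatever the dependence.

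**Never fewer rejections.** Holm's first threshold equals Bonferroni's and all later ones are larger. Any p-value at or below 0.05/m is therefore also rejected by Holm. Example with p = 0.02 and 0.04: Bonferroni-adjusted values are 0.04 and 0.08 (one rejection); Holm-adjusted values are 0.04 and 0.04 (two).

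**Gain in closed form, m = 2, independent, both effects real, 80% power alone.** The mean of each statistic is z(0.80) + z(0.975) = 2.80. Power at 0.025 is b = 0.7123; at 0.05 it is f = 0.80.
- Average power: Bonferroni b = 0.7123; Holm b + b(f − b) = 0.7123 + 0.7123 × 0.0877 = 0.7748.
- Both detected: b² = 0.5074 against b² + 2b(f − b) = 0.6323.
- No p-value passes the first step, so no gain: (1 − b)² = 0.0828.
- Only one effect real: the gain is 0.025 × (f − b) = 0.0022, or 0.2 points.

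**Other cases, by simulation (2,000,000 data sets each).** Average power with all effects real and 80% power alone:

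| Tests | Bonferroni | Holm, corr. 0 | Holm, corr. 0.5 | Holm, corr. 0.8 |
|---|---|---|---|---|
| 2 | 71.2% | 77.5% | 76.5% | 75.6% |
| 3 | 65.8% | 75.0% | 73.5% | 72.3% |

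The gains run from 75.6 − 71.2 = 4.4 to 75.0 − 65.8 = 9.2 points. At 50% power alone, two tests go from 38.9% to about 43% and three from 33.2% to 38–39%. With two tests, no p-value passes the first step in 8% to 20% of data sets at 80% power and in 37% to 51% at 50% power. No simulated data set had a Bonferroni rejection that Holm missed.

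**Realised error.** With one true null of two and the other effect real at 80% power, independent tests, family-wise error goes from 0.025 to 0.025 + 0.025b = 0.0428. By simulation Holm gives 4.1% at correlation 0.5 and 3.8% at 0.8. All are below 5%.

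**Why the family must not be enlarged.** Assume two CBCT measures with three contrasts each, and Bonferroni intended within each measure (0.05/3 = 0.0167). Holm over all six starts at 0.05/6 = 0.0083. A p-value of 0.010 with the other five above 0.05 passes the former and fails the latter. With six independent tests, three real at 80% power alone, pooled Holm has 59.6% average power against 65.8% for per-measure Bonferroni, and loses at least one rejection in about 17.6% of data sets. With all six real, pooled Holm gains (68.3%). Pooling also controls error over a larger set, so this is not a like-for-like comparison.

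**The false positive rate.** From the level and the count one can state a nominal bound (0.05), or, for independent true nulls, 1 − (1 − 0.05/m)^m: 0.0494 for m = 2 and 0.0492 for m = 3. The rate realised in the trial depends on which nulls are true, and that is unknown.

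**The case against.** The strongest case against is that Bonferroni is valid, and that the weightier gaps (undefined family, unnamed test, analyses chosen after seeing the data) exist under either method and are not repaired by Holm. That is correct. Holm, like Bonferroni, also needs valid p-values, which cannot be judged while the CBCT test is unnamed. If there is only one CBCT test, or none, the change does nothing. These limits stand; they reduce the point to an efficiency gain.

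A reader might infer more than the documents support:

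- *That the family is all CBCT comparisons pooled.* Sentence order suggests CBCT, but the correction could equally apply within each measure, or cover the histomorphometric tests that share the method. If it was meant within each measure, pooling can cost rejections, as shown above. The guarantee holds only for the family actually intended.
- *That the WHI, discomfort and PROM tests should be relabelled exploratory.* The plan tests them formally, and its closing list includes wound healing, discomfort and patient-reported satisfaction. Nothing in it ranks them below CBCT, and moving to Holm does not require it.
- *That the false-positive-rate clause is simply wrong.* A nominal bound can be calculated, and a false discovery rate may have been meant. The clause needs a definition rather than bare deletion.

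**Conclusion.** The point holds as a cheap improvement. In the same family, fixed beforehand and with valid p-values, Holm keeps the 0.05 family-wise bound under any dependence and never rejects fewer hypotheses; this does not depend on the number of tests. The size of the gain rests wholly on assumptions that the documents do not supply, and the 4 to 9 points come from the favourable case in which every effect is real. The documents do not support calling Bonferroni an error here.

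**What to change.** Replace the Bonferroni sentence with:

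> Within each family of comparisons to which the Bonferroni correction was to apply, fixed and counted before analysis and not enlarged, family-wise error is controlled at 0.05 by Holm's method, and Holm-adjusted p-values are reported.

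If the histomorphometric tests share the correction, they stay in that family. In place of the false-positive-rate clause, state the 0.05 family-wise bound; if a false discovery rate was meant, name it and its method. Leave the status of the WHI, discomfort and PROM tests as it is.

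**Cost.** No new participants or data, and no power lost within the same family. The authors must write down the intended family or families and name the test, which is needed for Bonferroni too. There are two downsides: simultaneous confidence intervals that match Holm are less simple than Bonferroni intervals, and realised family-wise error rises when some effects are real, while staying under 5%.

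### Kruskal-Wallis assumes independent groups, but the plan uses it to compare one cohort with itself across visits, so its p-values are off level and can miss real changes in healing and discomfort

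*Combined protocol and SAP*

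**What the plan says.** The Statistical Analysis Plan states that "Wound Healing Index (WHI) values obtained will be analyzed using the Kruskal-Wallis test" and gives the hypothesis: "The null hypothesis states that no differences in WHI will be found at different time points". It continues: "Likewise, the self-reported level of discomfort and PROMs will be compared using the Kruskal-Wallis test". For discomfort the roles of the variables are explicit: "The level of discomfort and the post-op visits will be the dependent and independent variable respectively". No grouping factor is named for PROMs, but the list of variables gives four collection visits for satisfaction (2 weeks, 6 weeks, final crown delivery, 1 year).

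Under Design, "This study is a cohort study". Under Methods, "consented subjects will undergo implant placement and immediate loading with a temporary crown". No comparison group is described anywhere, and no paired or repeated-measures method is named. The plan ends its account of methods with a general reservation that "suitability of appropriate analyses will be determined upon data distribution".

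**The concern.** The levels of the grouping factor are visits, and the same patients attend each of them. Kruskal-Wallis treats the scores at each visit as a separate, independent sample. It therefore leaves stable differences between patients in the error term, although they cancel when a patient is compared with himself or herself, and it refers the statistic to a distribution that holds only for independent groups.

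It is the only hypothesis test the plan names. The CBCT test is given only by reference to an unnamed histomorphometric test, and implant torque or stability values, marginal bone levels and mucosal outcomes are to be described. A non-significant result for wound healing or discomfort could then be read as no change between visits when the test had little chance of showing one.

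**Working it through.** The plan states no power or error figure to reproduce except the 0.05 significance level, so the check is whether the named test keeps that level and what power it gives up.

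**Inputs from the documents.** Visit as the grouping factor, one cohort, significance level 0.05, and four visits for satisfaction.

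**Assumptions.** Four visits for wound healing and discomfort as well (no count is given); 20 or 30 patients with complete data; a five-level score with equally likely levels at the midpoint of the change; a linear change from first to last visit; latent within-patient correlation ρ from 0 to 0.7, equal between all visits unless stated.

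**Step 1: why the level is wrong.** With n patients, k visits and N = nk ranks whose overall variance is S²,

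H = n Σⱼ (R̄ⱼ − (N+1)/2)² / S², referred to χ² on k−1 degrees of freedom.

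If the same patients supply every visit and their ranks correlate at ρ, the patient effect cancels from differences between visit means. The variance governing those differences is about S²(1−ρ)/n, yet the denominator still uses S². Under no change, H therefore behaves roughly as (1−ρ)χ². For k = 4 the critical value is 7.81, so the true level is about P(χ²₃ > 7.81/(1−ρ)):

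| ρ | 7.81/(1−ρ) | Approximate level |
|---|---|---|
| −0.2 | 6.51 | 8.9% |
| 0 | 7.81 | 5.0% |
| 0.1 | 8.68 | 3.4% |
| 0.3 | 11.16 | 1.1% |
| 0.5 | 15.63 | 0.14% |
| 0.7 | 26.05 | below 0.01% |

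The Friedman test ranks within each patient: Q = (k−1) n² Σⱼ (q̄ⱼ − (k+1)/2)² / A, where A is the sum over all patients and visits of (qᵢⱼ − (k+1)/2)². A patient's general level drops out before the test is formed.

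**Step 2: simulation.** Correlated normal scores were cut into five levels and both tests, with tie correction, were run on 10,000 data sets per setting. The null rates for Kruskal-Wallis cover n = 20 and 30. Power is Kruskal-Wallis vs Friedman.

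| ρ | Null rate, Kruskal-Wallis | 0.6 SD, n=20 | 0.6 SD, n=30 | 1.0 SD, n=20 |
|---|---|---|---|---|
| 0 | 4.7–4.8% | 30% vs 27% | 45% vs 41% | 73% vs 67% |
| 0.1 | 3.4% | 28% vs 30% | 43% vs 43% | 73% vs 70% |
| 0.3 | 1.2–1.5% | 22% vs 36% | 39% vs 53% | 72% vs 82% |
| 0.5 | 0.4% | 18% vs 48% | 34% vs 68% | 71% vs 92% |
| 0.7 | below 0.1% | 12% vs 68% | 28% vs 88% | 71% vs 99% |

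Friedman's null rate stayed at 4.5–5.0%. The simulated Kruskal-Wallis levels follow the approximation; they are somewhat higher at ρ = 0.5 mainly because cutting the scores into five levels weakens the latent correlation.

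**Step 3: sensitivity, n = 20.**
- *Change of 1.5 SD:* 98–99% vs 96–100%, so the loss is negligible.
- *Correlation decaying between visits (AR(1)), 0.6 SD:* 29% vs 28% (ρ = 0.1), 26% vs 30% (0.3), 24% vs 35% (0.5), 19% vs 46% (0.7).
- *Three visits, 0.6 SD:* 30% vs 30%, 27% vs 38%, 23% vs 48% and 18% vs 69% at the same four correlations.
- *Scores piled at one end (70/15/10/5% over four levels), 0.6 SD:* 15% vs 37% at ρ = 0.5 and 10% vs 52% at ρ = 0.7.
- *Negative correlation, ρ = −0.2, no change:* the Kruskal-Wallis level rises to about 8%.

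**The case against.** The strongest objection concerns importance. The stated objective is implant stability, survival, bone levels and soft-tissue outcomes, and most of these are to be reported descriptively. No primary endpoint, sample size or success criterion rests on Kruskal-Wallis. Under positive correlation the error is conservative, and the loss disappears at a correlation of about 0.1 or for a very large change. This stands as a limit on reach: the problem does not touch the descriptive outcomes. It does not rescue the named test, because each analysis to which the plan assigns it by name is affected, or for PROMs appears to be.

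Three further points have some force.
- The conservative direction depends on positive correlation. That is the usual case for repeated scores on one person, but the documents do not state it; at −0.2 the test rejects too often.
- The largest losses depend on the assumed setting. At ρ = 0.7 and 0.6 SD with n = 20, the loss is 68 − 12 = 56 points with equal correlation, 52 − 10 = 42 with skewed scores and 46 − 19 = 27 with decaying correlation.
- The only visit count in the documents belongs to satisfaction, the outcome whose grouping factor is least certain. The three-visit results show the same pattern.

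The reservation about data distribution makes the named tests provisional. Dependence, however, follows from the design and is known before any data exist. Kruskal-Wallis is already a rank test, so looking at the distribution gives no reason to leave it. The Bonferroni sentence follows the CBCT analysis, and a multiplicity correction would not repair dependence.

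**Conclusion.** The concern holds. For wound healing and discomfort the plan names a test for independent groups where the groups are the same patients; for PROMs the wording points the same way without saying so. The p-values are not at their stated level whenever scores within a patient are correlated. With positive correlation the consequence is lost power, not excess false positives.

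The size cannot be fixed from the documents. Under the stated assumptions it runs from none (correlation of 0.1 or less, or a 1.5 SD change), through 48 − 18 = 30 points (correlation 0.5, 0.6 SD, n = 20), to more than 50 points (equal correlation of 0.7, 0.6 SD). This is an analysis that is wrong as written and should be corrected before the data are analysed.

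**What to change.** Replace Kruskal-Wallis with a within-patient analysis for the wound healing index, discomfort and any PROM compared across visits. Name one of these as the planned analysis:
- an ordinal (cumulative-link) mixed model with visit as fixed effect and patient as random intercept; or
- the Friedman test, followed by Wilcoxon signed-rank comparisons between visits with Holm adjustment.

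List the visits compared for each outcome, including the PROMs, where the factor is now unstated.

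The cost is a change of wording. It uses visit data already planned and adds no visits or measurements. The mixed model keeps patients who miss a visit but may fail to converge with few patients or sparse score levels, so if it is chosen, Friedman should be written in as the fallback. Friedman uses only patients with every visit. If within-patient correlation were near zero it would also lose a few points of power: at n = 20, 27% instead of 30% for 0.6 SD and 67% instead of 73% for 1.0 SD. The mixed model was not simulated, so the gains shown are Friedman's, with complete data.

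### Wound healing and discomfort are compared across visits with a test for independent, unordered groups, with no paired analysis, visit contrasts or estimates of change

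*Combined protocol and SAP*

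**What the plan says.** The Design paragraph describes one cohort, and no comparison arm is described, so a comparison over visits is a comparison within the same people.

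For healing, the Statistical Analysis Plan states: "Wound Healing Index (WHI) values obtained will be analyzed using the Kruskal-Wallis test". The hypothesis attached to it is "The null hypothesis states that no differences in WHI will be found at different time points". Discomfort and the other patient-reported outcomes follow the same route: "Likewise, the self-reported level of discomfort and PROMs will be compared using the Kruskal-Wallis test". For discomfort the roles are given as "The level of discomfort and the post-op visits will be the dependent and independent variable respectively", and then "The significance level will be set at 0.05".

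No paired test, visit-to-visit comparison or estimate of change is named for WHI or discomfort. The sentence promising descriptive statistics concerns the other clinical variables. Visits are listed only for satisfaction: "Patient-reported outcome measures of satisfaction collected at 2-week, 6-week, Final Crown Delivery, 1-Year Visit". No sample size, effect size or power is stated.

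**The concern.** Two properties of Kruskal-Wallis do not fit this design.

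- **Independence.** The test assumes that every value comes from a different person. Here each patient contributes one value per visit. Stable differences between patients count as noise, although comparing each patient with himself or herself would remove them.
- **No direction or timing.** Visit is only a label. If the visits were shuffled, the p-value would not change. Rejecting the null would not support a statement that discomfort fell, or that healing was complete by a given visit.

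The plan could therefore miss a real change. If it found one, it would have no pre-specified way to describe it. The descriptions would then be chosen after the data had been seen.

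**Working it through.** **Inputs.** From the documents: Kruskal-Wallis, visit as the grouping factor, alpha 0.05, one cohort. Assumed, because not stated: n = 20 patients; k = 4 visits (the number listed for satisfaction), with 3 to 6 as a range; within-patient correlation ρ = 0.5. The plan has no power figure to reproduce.

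**Step 1: false-positive rate of the planned test.** With equal correlation ρ between visits, the variance of a difference between two visit means is 2σ²(1−ρ)/n. Kruskal-Wallis behaves as if it were 2σ²/n. Under the null its statistic is then roughly (1−ρ) times a chi-square on k−1 = 3 degrees of freedom, whose 5% point is 7.815.

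- ρ = 0.3: P(χ²₃ > 7.815/0.7 = 11.16) ≈ 1.1%
- ρ = 0.5: P(χ²₃ > 7.815/0.5 = 15.63) ≈ 0.1%

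Simulation with n = 20 and four visits gave 5.2% at ρ = 0, 1.4% at 0.3, 0.2% at 0.5 and about 0% at 0.7. Friedman stayed at 4.4% to 4.8%. The two routes agree: the planned test is conservative, not liberal.

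**Step 2: power for a steady change.** Model: score = patient effect N(0,1) + residual N(0,1) + slope × visit, rounded to half-SD categories. This gives ρ = 1/(1+1) = 0.5. The slope is 0.30 residual SD per visit.

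| Test | Uses pairing | Uses order | Power |
|---|---|---|---|
| Kruskal-Wallis (planned) | no | no | 22.5% |
| Friedman | yes | no | 56.5% |
| Page, two-sided | yes | yes | 75.2% |

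The total gap is 75.2 − 22.5 = 52.7 points. Pairing accounts for 56.5 − 22.5 = 34.0 and order for 75.2 − 56.5 = 18.7.

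A second setting (ρ = 0.5, linear change of 0.6 SD in total over the four visits) gave 19.1%, 49.5% and 67.2%. Pairing accounts for 49.5 − 19.1 = 30.4 points and order for 67.2 − 49.5 = 17.7.

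**Step 3: how far the order component can go.** For a purely linear change, compare a 1-df trend test with a (k−1)-df omnibus test at the same noncentrality λ: loss = P(χ²₁(λ) > c₁) − P(χ²ₖ₋₁(λ) > cₖ₋₁), where c is the 5% point of each central distribution. The maximum over λ, in large samples, is:

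| Visits | Maximum loss (points) |
|---|---|
| 3 | 10.5 |
| 4 | 17.0 |
| 5 | 21.8 |
| 6 | 25.5 |

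The small-sample F version for four visits gives 20.1 (n = 10), 18.5 (n = 20) and 18.0 (n = 30).

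**Step 4: other shapes of change (n = 20, four visits).**

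| Shape | Friedman | Page |
|---|---|---|
| Step of 0.6 SD after visit 1, then plateau | 35% | 35% |
| Step of 0.9 SD after visit 1, then plateau | 70.5% | 63.7% |
| Rise of 0.75 SD and full return | 67.1% | 3.8% |

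The advantage of an ordered test disappears for the small step and reverses for the other two shapes.

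**The case against.** The strongest defence is that the stated null hypothesis is an omnibus one, and an omnibus test answers it. No steady trend is hypothesised anywhere. That stands: using an unordered test is not in itself an error. It does not rescue the choice of Kruskal-Wallis, because an omnibus question about the same patients still calls for a paired test.

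A reader might infer that the plan gives up about 19 points of power by ignoring visit order. The documents do not support that as a statement about this trial. The figure is the gap between Page and Friedman, and the plan does not use Friedman. It also assumes four visits and equal steps, and it is not a ceiling (Step 3).

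A reader might also infer that Page's test should become the primary test. That is a trade-off, not a correction (Step 4). If the satisfaction visits also apply to healing and discomfort, they are very unevenly spaced: 2 weeks, 6 weeks, crown delivery at about 3 months, and a year after that. Early change followed by a plateau is then at least as plausible as equal steps.

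Two clauses might seem to cover the gap. The first, "The Bonferroni method for correction will be applied and the false positive rate will be calculated", directly follows the imaging sentence and is tied to no comparison of visits. The second, "the data will be assessed upon collection and suitability of appropriate analyses will be determined upon data distribution", names no alternative and postpones the choice until the data are in hand.

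Finally, if scores within a patient were uncorrelated, Kruskal-Wallis would hold its level and slightly beat Friedman (31.9% against 25.7% for the 0.6 SD linear change). Zero correlation is unlikely for repeated self-reports or healing scores from one person, but the documents give no figure.

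**Conclusion.** The point holds in two parts.

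The first needs no assumed numbers. Followed as written, the plan cannot show the direction or timing of change in WHI or discomfort, and its test ignores that the visits are repeated on the same patients.

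The second is the size of the loss, which is conditional. At n = 20, four visits, correlation 0.5 and 0.30 SD per visit, power is about 23%, against 57% for a paired omnibus test. That loss of roughly 34 points comes from ignoring the pairing and is the larger part. Ignoring order costs a further 17 to 19 points in the four-visit linear case. Its maximum runs from about 10 to 26 points for three to six visits, and it can be zero or negative for an early step. The documents fix none of these inputs, so the figures illustrate scale only.

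**What to change.** In the Statistical Analysis Plan, for WHI and discomfort:

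- List the visits at which each is recorded, and state the sample size.
- Replace Kruskal-Wallis with the Friedman test over visits within patient, two-sided alpha 0.05 for each outcome.
- Pre-specify paired Wilcoxon signed-rank comparisons of consecutive visits (three if there are four visits), Holm-adjusted and reported whatever the global result. Give each with the Hodges-Lehmann median change and its 95% confidence interval.
- If monotone change is expected, add Page's ordered test as a pre-specified secondary trend test. State that it has almost no power against a rise and full return.

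The cost is some wording, a few lines of code, a few more analyses and one multiplicity adjustment. No new data are needed. Friedman uses only patients seen at every visit, so the number of complete patients should be reported; each paired comparison can use everyone with both of its visits.
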